Figure 14.2.3.3.2.5	Box Plot of AUC _{0-t} by Parent and Metabolites for Visit 10 (25 mg/kg/day), Age 18 to 65 Years	Safety Analysis Set
Figure 14.2.3.4.1.1	Box Plot of AUC _{0-t} by Parent and Metabolites for Visit 3 (50 mg/kg/day)	Safety Analysis Set
Figure 14.2.3.4.1.2	Box Plot of AUC _{0-t} by Parent and Metabolites for Visit 3 (50 mg/kg/day), Age 1 to 6 Years	Safety Analysis Set
Figure 14.2.3.4.1.3	Box Plot of AUC _{0-t} by Parent and Metabolites for Visit 3 (50 mg/kg/day), Age 7 to 11 Years	Safety Analysis Set
Figure 14.2.3.4.1.4	Box Plot of AUC _{0-t} by Parent and Metabolites for Visit 3 (50 mg/kg/day), Age 12 to 17 Years	Safety Analysis Set
Figure 14.2.3.4.1.5	Box Plot of AUC _{0-t} by Parent and Metabolites for Visit 3 (50 mg/kg/day), Age 18 to 65 Years	Safety Analysis Set
Figure 14.2.3.4.2.1	Box Plot of AUC _{0-t} by Parent and Metabolites for Visit 10 (25 mg/kg/day)	Safety Analysis Set
Figure 14.2.3.4.2.2	Box Plot of AUC _{0-t} by Parent and Metabolites for Visit 10 (25 mg/kg/day), Age 1 to 6 Years	Safety Analysis Set
Figure 14.2.3.4.2.3	Box Plot of AUC _{0-t} by Parent and Metabolites for Visit 10 (25 mg/kg/day), Age 7 to 11 Years	Safety Analysis Set
Figure 14.2.3.4.2.4	Box Plot of AUC _{0-t} by Parent and Metabolites for Visit 10 (25 mg/kg/day), Age 12 to 17 Years	Safety Analysis Set
Figure 14.2.3.4.2.5	Box Plot of AUC _{0-t} by Parent and Metabolites for Visit 10 (25 mg/kg/day), Age 18 to 65 Years	Safety Analysis Set

Table 22 List of OLE Phase Figures

Figure Number	Title	Analysis Set
OLE Figure 9.1.1	Percentage Change in TSC-associated Seizure Frequency Over Time	OLE Safety Analysis Set
OLE Figure 9.1.2	Percentage Change in TSC-associated Seizure Frequency Over Time (LOCF)	OLE Safety Analysis Set

OLE Figure 9.1.3	Percentage Change in TSC-associated Seizure Frequency Over Time (Patients with Data in OLE Week 37 to 48)	OLE Safety Analysis Set
OLE Figure 9.2.1	Percentage Change in Total Seizure Frequency Over Time	OLE Safety Analysis Set
OLE Figure 9.2.2	Percentage Change in Total Seizure Frequency Over Time (LOCF)	OLE Safety Analysis Set
OLE Figure 9.2.3	Percentage Change in Total Seizure Frequency Over Time (Patients with Data in OLE Week 37 to 48)	OLE Safety Analysis Set

GW Research Ltd.

Trial Code: GWEP1521

**A DOUBLE-BLIND, RANDOMIZED, PLACEBO-CONTROLLED
STUDY TO INVESTIGATE THE EFFICACY AND SAFETY OF
CANNABIDIOL (GWP42003-P, CBD) AS ADD-ON THERAPY IN
PATIENTS WITH TUBEROUS SCLEROSIS COMPLEX WHO

1. INTRODUCTION

This document is an addendum to the statistical analysis plan (SAP) for trial GWEP1521, Version 2 dated 24th April 2019 (hereinafter referred to as the main SAP). This addendum consists of descriptions for a number of post-hoc analyses to support a summary of clinical efficacy.

2. STATISTICAL METHODS

2.1 General Considerations

Unless otherwise stated, the statistical reporting definitions and considerations as stated in the main SAP will also apply to this addendum.

All analyses and summaries will be produced using SAS[®] Version 9.4.

2.2 Analysis Sets

The intention to treat (ITT) analysis set as defined in the main SAP will be the primary analysis set for all endpoints.

2.3 Efficacy Analysis

2.3.1 General Approach

Statistical hypothesis testing will be performed as appropriate. However, no formal adjustment of statistical significance for multiple testing will be performed, although the multiplicity should be allowed for when interpreting the results.

All statistical tests will be 2-sided and use the 5% significance level.

2.3.2 Cumulative Distribution Function Plots of Percent Reduction in Seizure Frequency

Cumulative distribution plots plotting the percent reduction against the cumulative proportion of patients achieving that level of reduction, as described in the main SAP, will be generated for the following:

- Patients taking clobazam.
- Patients not taking clobazam.

The above will be generated for TSC-associated seizures during the blinded phase treatment period.

2.3.3 Robustness to Withdrawn Patients

There were higher proportions of patients in each treatment arm that withdrew during the blinded phase treatment period when compared with placebo. In order to assess the robustness of the results, 2 analyses in the following sections are proposed.

2.3.3.1 Time to 10th and 20th Seizure

Time from Day 1 to a patient experiencing their 10th and 20th or more seizure will be calculated as follows:

Date criterion was achieved – Date of Day 1 – Number of unreported days in IVRS between Day 1 and date criterion was achieved + 1

Patients who complete the blinded phase without experiencing greater than or equal to the corresponding number of seizures, or who withdraw from the blinded phase, will be censored at the earliest of:

- Day 113.
- The last recorded seizure day during the blinded phase treatment period.

The exact day used for censoring will be the day obtained from above minus the number of unreported days in IVRS between Day 1 and the day obtained from above.

The advantage of this proposed time to event analysis is that it is distinctly less sensitive to early withdrawals.

The time to corresponding event will be summarized on a continuous scale, by treatment arm. The lower and upper quartiles will also be presented along with the number of events and number of patients censored. In addition, the hazard ratio and 95% confidence interval, from a Cox proportional hazards model including treatment arm and stratified age group as covariates, will be presented along with a p-value from a log-rank test. A corresponding Kaplan-Meier plot will also be produced for both TSC-associated seizures and total seizures.

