5. STATISTICAL METHODS

5.1 General Considerations

In all tables, listings and figures for the double-blind phase, the trial medications will be referred to and labelled as per Table 1.

Table 1 Blinded Phase Trial Treatments

Endpoint	Actual Treatment	Treatment Label
Efficacy	Pooled Placebo	Placebo
Safety	25 mg/kg/day Placebo	Placebo 25 mg/kg
	50 mg/kg/day Placebo	Placebo 50 mg/kg
All	25 mg/kg/day GWP42003-P	25 mg/kg
All	50 mg/kg/day GWP42003-P	50 mg/kg

For safety tables where placebo is split by dosing volume, an additional Pooled Placebo column will be included.

For OLE tables, columns will be included for treatment received during the double-blind phase (GWP42003-P or placebo, i.e. not split by dose) and overall.

In all tables, listings and figures, the trial visits will be referred to and labelled as per Table 2.

Table 2 Trial Visits

Actual Visit	Visit Label
Visit 1: Screening	Day -35
Visit 2: Day -28, baseline visit	Day -28
Visit 3: Day 1, Randomization	Day 1
Visit 4: Day 15	Day 15
Visit 5: Day 29	Day 29
Visit 6: Day 43	Day 43
Visit 7: Day 57	Day 57
Visit 8: Day 71, Telephone	Day 71
Visit 9: Day 85	Day 85
Visit 10: Day 113	End of Treatment
Visit 11: Day 123	End of Taper
Visit 12: Day 151	Safety Follow-Up
Visit B1: Day 1, Enrollment	OLE Day 1
Visit B2: Day 15	OLE Day 15
Visit B3: Day 36	OLE Day 36
Visit B4: Day 92	OLE Day 92
Visit B5: Day 141, Re-stocking of supplies	OLE Day 141
Visit B6: Day 183	OLE Day 183
Visit B7: Day 232, Re-stocking of supplies	OLE Day 232
Visit B8: Day 274	OLE Day 274
Visit B9: Day 323, Re-stocking of supplies	OLE Day 323
Visit B10: Day 365	OLE End of Treatment
Visit B11: Day 375	OLE End of Taper
Visit B12: Day 389	OLE Post-taper Safety Telephone Call
Day 403	OLE Follow-Up

Unless stated otherwise, continuous variables will be summarized showing the number of non-missing values (n), mean, standard deviation, median, minimum and maximum and categorical variables will be summarized showing the number and percentage of patients falling in each category. For continuous summaries of seizure frequency, the lower and upper quartiles will also be presented.

Minimum and maximum values will be presented to the same decimal precision as the raw data. Mean and median will be presented to one more decimal place than the raw data, and standard deviation to 2 more decimal places than the raw data. Percentages will be presented to one decimal place.

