5.1.3.4 Treatment Period

The treatment period of the double-blind phase is defined as Day 1 to Day 113.

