5.5.4.10 Time to Baseline TSC-associated Seizure Frequency

Blinded Phase only:

Time to baseline TSC-associated seizure frequency is defined as the number of reported days in IVRS, from Day 1, that it takes for the cumulative number of TSC-associated seizures experienced to be greater than or equal to the number of seizures (per 28 days) experienced during the baseline period and will be calculated as:

Date criterion was achieved – Date of Day 1 – Number of unreported days in IVRS between Day 1 and date criterion was achieved + 1

Patients who complete the trial without experiencing greater than or equal to the number of seizures (per 28 days) experienced during the baseline period, or who withdraw from the trial, will be censored at the earliest of:

- Day 99.
- The date of last dose as recorded on the ‘End of Treatment Study Outcome’ CRF page.

The exact day used for censoring will be the day obtained from above minus the number of unreported days in IVRS between Day 1 and the day obtained from above.

Time to baseline TSC-associated seizure frequency will be summarized on a continuous scale, by treatment arm, for patients in the ITT analysis set. The lower and upper quartiles will also be presented. The Kaplan-Meier estimates for the median time to baseline TSC-associated seizure frequency will be presented along with 95% CIs for the median and p-values from log-rank tests comparing each GWP42003-P arm with placebo. A Kaplan-Meier plot will also be produced.

The above will be repeated using Day 29 instead of Day 1 as the start day for counting the cumulative number of TSC-associated seizures.

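### Addendum 2.3.3.1 summarizes a right-censored time to the 10th or 20th seizure with ordinary medians and quartiles, which come out too short; Kaplan-Meier percentiles should replace them

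*SAP*

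**What the plan says.** Section 2.3.3 of the addendum gives its reason for further analysis: "There were higher proportions of patients in each treatment arm that withdrew during the blinded phase treatment period when compared with placebo". Section 2.3.3.1 then defines the time to the 10th and 20th seizure. Patients who finish the blinded phase without the event, "or who withdraw from the blinded phase, will be censored at the earliest of" Day 113 and a second limit: "The last recorded seizure day during the blinded phase treatment period". In the main SAP, "The treatment period of the double-blind phase is defined as Day 1 to Day 113".

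On reporting, the addendum says "The time to corresponding event will be summarized on a continuous scale, by treatment arm", and then "The lower and upper quartiles will also be presented along with the number of events and number of patients censored". The comparison between arms uses a Cox hazard ratio with its confidence interval, a log-rank p-value and Kaplan-Meier plots. No Kaplan-Meier median or quartile is listed, either in that section or in the addendum's list of tables and figures.

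Section 2.1 of the addendum carries over the main SAP's reporting conventions unless it states otherwise. Section 5.1 of the main SAP sets the convention: "continuous variables will be summarized showing the number of non-missing values (n), mean, standard deviation, median, minimum and maximum".

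The parallel endpoint in the main SAP, Section 5.5.4.10, uses the same phrase: "Time to baseline TSC-associated seizure frequency will be summarized on a continuous scale, by treatment arm, for patients in the ITT analysis set". It adds quartiles and then, as a separate item, the Kaplan-Meier median with a 95% CI.

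**The concern.** An ordinary median of a right-censored time does not estimate the median time to event. Section 5.5.4.10 shows that in this SAP a continuous-scale summary is something other than a Kaplan-Meier estimate, because both are listed there. The addendum keeps the first and drops the second, so the only median planned for its tables is the ordinary one.

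Section 2.3.3.1 was added because more patients withdrew from the active arms, and it presents the time-to-event approach as less sensitive to early withdrawal. The medians and quartiles in its tables would nevertheless move with withdrawal if censoring days are kept. They could also disagree with the Kaplan-Meier plot and hazard ratio shown beside them. The addendum supports a summary of clinical efficacy, where a tabulated median may well be quoted.

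**Working it through.** The plan states no figure for these times, so there is nothing to reproduce. The check has three steps.

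**1. Direction.** Let T be the time to the event and C the censoring time. If censoring days are kept as values, the summarized variable is X = min(T, C). With C independent of T,

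P(X > t) = P(T > t) × P(C > t) ≤ P(T > t).

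Every quantile of X is therefore at or below the same quantile of T, and the gap widens as withdrawal rises. In 3,000 simulated samples of 70 patients, the ordinary quartiles never exceeded the Kaplan-Meier quartiles. If only patients with events are used, the summary is conditional on the event occurring within follow-up. It is then too short even with no withdrawals, because completers without the event drop out.

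**2. Size.** The SAP gives neither withdrawal percentages nor seizure rates, so all rates here are assumed. The simulation used 200,000 patients per scenario, lognormal patient seizure rates (log-SD 1), withdrawal uniform over Days 1–112 and otherwise censoring at Day 113. Rates are median seizures per 28 days. All results are medians in days.

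| Scenario | Withdrawal | Kaplan-Meier | Censoring days kept | Events only |
|---|---|---|---|---|
| 20th seizure, rate 8, same in both arms | 5% | 69 | 66 | 45 |
| same | 20% | 69 | 59 | 44 |
| 10th seizure, rate 8 halved by treatment | 20% | 67 | 58 | 42 |
| 20th seizure, rate 20 halved | 0% | 55 | 55 | 41 |
| same | 20% | 55 | 49 | 38 |
| 10th seizure, rate 20, same in both arms | 5% | 14 | 14 | 13 |
| same | 20% | 14 | 13 | 13 |
| 10th seizure, rate 57 halved | 20% | 10 | 10 | 10 |

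The first two rows can be checked by hand. Log T is roughly normal around log 69. Its SD is √(1 + 0.051) = 1.025, where 0.051 is the variance of the log of a gamma variable with shape 20.
- At 20% withdrawal and t = 59: P(T > 59) = Φ(ln(69/59)/1.025) = 0.561; P(C > 59) = 1 − 0.20 × 59/112 = 0.895; product 0.502.
- At 5% withdrawal and t = 66: P(T > 66) = Φ(ln(69/66)/1.025) = 0.517; P(C > 66) = 1 − 0.05 × 66/112 = 0.971; product 0.502.

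Both products are close to one half, so 59 and 66 are the ordinary medians. Two arms with identical true distributions would show a difference of 66 − 59 = 7 days, produced by withdrawal alone.

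A second model used Weibull times (shape 1.5) with 15% withdrawing uniformly over Days 1–60.
- True median 60: at t = 51.7, exp(−ln 2 × (51.7/60)^1.5) × (1 − 0.15 × 51.7/60) = 0.574 × 0.871 = 0.500. The shortfall is 60 − 51.7 = 8.3 days. The events-only median is about 49.
- True median 90: at t = 75, 0.590 × 0.85 = 0.502. The shortfall is about 15 days.

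**3. Upper quartile.** In the first two rows of the table the true upper quartile is about 137 days and Kaplan-Meier does not reach it. The ordinary summary prints 113 with censoring days kept, and 71 or 69 with events only.

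**The case against.** The strongest objection is that nothing inferential depends on this summary. The hazard ratio, log-rank test and Kaplan-Meier plots all handle censoring, and a median can be read from the plots. The analyses are post hoc. A shorter time in the active arms works against the drug and cannot create false evidence of benefit. All of this stands, and it limits the point to minor severity.

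A reader might infer that the addendum counts censored times as event times. It does not say so. It reports events and censored patients as separate counts and is silent on how the censored enter the summary. Quartiles beside such counts are also a familiar layout for survival output, so a programmer might produce Kaplan-Meier quartiles. The adopted convention in Section 5.1 and the separate Kaplan-Meier item in Section 5.5.4.10 point the other way. Both ordinary readings are too short, so the point does not depend on choosing between them.

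A reader might also infer that only the arms with more withdrawals are affected, or that the treatment difference shrinks by a fixed percentage. Neither is supported. Any arm with censoring can be affected, the events-only reading needs no withdrawals, and the percentage follows entirely from assumed rates.

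Section 5.5.4.10 is largely covered, because its Kaplan-Meier median is tabulated. Only its quartiles lack a named estimator.

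**Conclusion.** The point holds as a minor descriptive-reporting error in Section 2.3.3.1 of the addendum. Read with Section 5.1 of the main SAP, the plan puts ordinary medians and quartiles of a right-censored time in the tables. It does not say how censored patients enter and provides no Kaplan-Meier median.

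Both ordinary readings understate the times. With censoring days kept, the shortfall grows with withdrawal, which the addendum reports as higher in the active arms. The shortfall in the median is then about 0 to 1 day when seizures are frequent, and roughly 8 to 15 days in low-rate scenarios with 15 to 20% withdrawal. An unreached upper quartile appears as 113 or less. These sizes rest on assumed seizure rates, withdrawal rates and timing, and on withdrawal unrelated to seizure time. They are illustrations and not estimates for this trial. The comparative results do not depend on this summary.

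**What to change.** In Section 2.3.3.1 of the addendum, replace the ordinary median and quartiles with Kaplan-Meier estimates of the 25th, 50th and 75th percentiles and their 95% CIs by arm, shown as 'not reached' where applicable, beside the planned numbers of events and censored patients. If any ordinary summary is kept, label it as not adjusted for censoring and say which patients it includes.

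In Section 5.5.4.10, state only that the quartiles are also Kaplan-Meier estimates.

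The cost is one sentence in each section. Standard survival output already supplies these percentiles, and no new data or tests are needed.

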5.5.2 Primary Efficacy Endpoint

Blinded Phase:

The primary endpoint is the change in number of TSC-associated seizures (see Section 5.1.3.7) during the treatment period (see Section 5.1.3.4) compared to baseline period (see Section 5.1.3.1) in patients taking GWP42003-P compared with placebo.

The primary endpoint will be analyzed using a negative binomial regression model with the total number of TSC-associated seizures during the baseline period and treatment period as the response variables.

A mixed effect model with repeated measures will be performed modelling the observed total number of TSC-associated seizures in the baseline period and treatment period implemented within the framework of general linear models using the negative binomial response distribution. The model will include stratified age group (1–6 years, 7–11 years, 12–17 years and 18–65 years), time, treatment arm and treatment arm by time interaction as fixed effects and patient as a random effect. The log transformed number of days in which seizure data were reported will be included as an offset. The time variable corresponds to an indicator for the baseline period and treatment period.

The GLIMMIX procedure in SAS will be utilized to perform the analysis with the option `maxopt=300` applied. If the model fails to converge, then the statement `'nloptions tech=nr ridge;'` will be added. If convergence is still not achieved, then `'method=laplace'` will be utilized. However, if convergence is still not possible, then the model will be changed to utilize the log normal response distribution (log rate model). If the log rate model is required and there are patients with no seizures during the baseline or treatment period then all patients will have their baseline and treatment period seizure count adjusted by adding a value of 1.

The estimated least squares mean seizure rate for each period and the estimated ratio of least squares means for treatment period to baseline period and 95% confidence intervals (CIs) will be presented for each treatment arm. In addition, the estimated ratio of each GWP42003-P arm to placebo and 95% CIs will be presented along with the p-value testing the null hypothesis that this ratio is 1.

For each ratio and upper and lower bound of the 95% CI, the percentage reduction will also be presented, calculated as:

$$[1 - (X \div Y)] \times 100\%$$

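### The addendum's time to 10th and 20th seizure analysis takes no account of baseline seizure frequency, which costs precision, and its censoring date is ambiguous

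*SAP*

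**What the plan says.** Section 2.3.3 of the SAP addendum explains why two further analyses were added: "There were higher proportions of patients in each treatment arm that withdrew during the blinded phase treatment period when compared with placebo". The first of the two is section 2.3.3.1: "Time from Day 1 to a patient experiencing their 10th and 20th or more seizure will be calculated as follows". The threshold is the same for every patient, and the analysis is run for TSC-associated and for total seizures. The hazard ratio and its interval are taken "from a Cox proportional hazards model including treatment arm and stratified age group as covariates", and they "will be presented along with a p-value from a log-rank test". No stratification of that test is mentioned.

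Patients without the event, whether they completed or withdrew, are censored at the earlier of Day 113 and "The last recorded seizure day during the blinded phase treatment period". Unreported IVRS days are then subtracted. The section states its merit as follows: "The advantage of this proposed time to event analysis is that it is distinctly less sensitive to early withdrawals".

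The main SAP uses baseline in comparable places. The primary model (5.5.2) takes the "total number of TSC-associated seizures during the baseline period and treatment period as the response variables", with patient as a random effect. The ANCOVA sensitivity analyses (5.5.2.1) include baseline. The existing time-to-event analysis (5.5.4.10) counts the event when the cumulative number is "greater than or equal to the number of seizures (per 28 days) experienced during the baseline period", so its threshold is scaled to the patient.

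**The concern.** How quickly a patient reaches a fixed number of seizures depends first on how often that patient has seizures anyway. If baseline frequency is absent from the covariates, the strata and the threshold, that between-patient spread stays in the comparison as noise. The purpose of the analysis is reassurance about unequal withdrawal. With a noisy test, a non-significant result could not be told apart from a real weakness.

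The censoring date raises a second, smaller matter. If it means the last day on which a seizure occurred, then the better a patient without the event does, the earlier that patient leaves the risk set. Someone with 9 seizures by Day 30 and none afterwards would be censored at Day 30 although observed to Day 113.

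**Working it through.** **1. The plan's own figure.** The addendum states no power, hazard ratio or event count for this analysis. The only benchmark is section 3.2 of the main SAP: 70 per arm, mean reductions of 15% and 50%, SD 60%, two-sided 5% Mann-Whitney-Wilcoxon test, 90% power. By Noether's formula, P(X<Y) = Φ(35/(60√2)) = Φ(0.412) = 0.660. Then N = (1.960 + 1.282)² / (12 × 0.25 × 0.160²) = 10.51/0.0768 = 136.8, or 69 per arm. At 70 per arm, power is Φ(√(140 × 0.0768) − 1.960) = Φ(1.319) = 90.6%. The stated 90% reproduces. The same assumptions imply a rate ratio of 0.50/0.85 = 0.588.

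**2. Why baseline matters.** At a constant rate, the expected time to the 10th seizure is 10 × 28/(baseline per 28 days × period multiplier). With assumed baselines of 15 and 60 per 28 days:

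- Placebo (× 0.85): 280/12.75 = 22.0 days and 280/51 = 5.5 days.
- Active (× 0.50): 280/7.5 = 37.3 days and 280/30 = 9.3 days.

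Treatment changes the time by a factor of 1.7. A fourfold difference in baseline changes it by a factor of 4.

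**3. Simulated size.** Two simulations were run with 70 per arm and Poisson counts. Baselines, patient noise and withdrawal are assumptions in both.

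| | Simulation A | Simulation B |
|---|---|---|
| Treatment/baseline ratio | medians 0.75 and 0.50 | 0.85, rate ratio 0.588 |
| Patient noise (log-SD) | 0.7 | 0.5 |
| Median baseline per 28 days | 20-100 | 15, 30, 60 |
| Baseline log-SD | 0.7-1.3 | 0.8, 1.2 |
| Withdrawal | none described | 15% active, 3% placebo |
| HR without baseline | 0.66-0.79 | 0.56-0.69 |
| HR with log baseline | 0.56-0.64 | 0.37-0.45 |
| Power without baseline | 27-61% | 53-82% |
| Power with log baseline | 68-88% | 98-100% |

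In B, the fit on arm alone, whose test is close to the log-rank, had 54-83% power. The levels differ because the effect and noise differ: A's mean ratios are 0.75 × e^0.245 = 0.96 and 0.50 × e^0.245 = 0.64, a rate ratio of 0.67 against 0.588. The direction is the same in both.

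**4. No treatment effect.** In B's 12 null scenarios (400 runs each; Monte Carlo SE about √(0.05 × 0.95/400) = 1.1 points), the arm-plus-age model rejected in 3-6% of runs. The baseline-adjusted model rejected in 3-9%, averaging 76/12 = 6.3%. A small part of its apparent power may therefore be a slightly liberal Wald test.

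**5. Literal censoring day (simulation B).** Patients without the event lose 4-22 days of observed follow-up on average. With a homogeneous effect, the arm-plus-age HR moves by at most 0.02 and power falls by 0-6 points. A variant assumed that 10-20% of active patients become nearly seizure-free after week 1 (one fifth of that share on placebo), with baseline log-SD 1.2. The loss was then 25-62 days, the HR moved from 0.52-0.64 to 0.62-0.68, and power fell from 69-89% to 50-70%. With baseline in the model, the fall was at most 2 points, though power was near its ceiling. The variant censored patients with no seizures (0.3-3.3% of patients) at Day 1, which somewhat overstates the cost.

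**The case against.** Randomization balances baseline in expectation, so leaving it out costs precision and not validity. A hazard ratio averaged over baseline is also a different quantity from one conditional on baseline. Both statements stand. A reader might infer that the written hazard ratio is simply biased towards 1, or that the result could mislead in favour of the drug. The documents support neither: part of the difference is marginal versus conditional estimand, and the test does not over-reject.

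The addendum calls itself post hoc and sets no power target. A reader might therefore call the analysis underpowered, but no standard has been set for it to miss. The 90% belongs to another test of another variable. The loss is relative to the adjusted analysis.

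This is also not the only protection against withdrawal. The main SAP has placebo-based multiple imputation with a tipping-point analysis (5.5.2.1.1) and the baseline-scaled time-to-event analysis (5.5.4.10). Addendum section 2.3.3.2 repeats the primary model with withdrawn active patients penalized. That limits the stakes. It does not make this check more informative.

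On censoring, the disputed phrase can fairly be read as the last day with seizure data recorded, since the next sentence works in IVRS reporting days. Informative censoring cannot then be asserted as fact; ambiguity can. Nor does a completer with no seizures lack a date, because the rule defaults to Day 113. The gap concerns a withdrawn patient with no seizures, for whom Day 113 lies beyond observation. Subtracting unreported days repairs that only if days after withdrawal count as unreported, which is not stated.

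**Conclusion.** The point holds as a loss of precision. The fixed-count analysis ignores information that the trial has already collected and that the main SAP uses elsewhere, so a non-significant result would be hard to interpret. The error is conservative and does not inflate the type I error.

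Across the two simulations, power was about 27-82% without baseline and 68-100% with it. The SAP gives no baseline distribution, patient-level variability or withdrawal rates, so these ranges illustrate the direction and do not estimate this trial's power. If age group predicts baseline frequency, the existing age term would narrow the gap somewhat.

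The censoring wording is a separate, lesser defect. On the literal reading it discards observed seizure-free follow-up, with little effect unless a sizeable share of active patients become nearly seizure-free early. On the other reading only clarification is needed.

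**What to change.** In addendum section 2.3.3.1, do one of the following.

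- Add log baseline seizure frequency per 28 days, for the seizure class being analysed, to the Cox model (adding 1 for all patients if zeros occur, as 5.5.2.1 of the main SAP does). Take the p-value from that model. Adding the covariate while keeping the unadjusted log-rank p-value would leave the test unchanged. A robust variance is a sensible precaution given the null results above.
- Stratify the log-rank test by age group and baseline tertile. Section 5.5.5 already defines tertiles for TSC-associated seizures; total seizures need their own. The 4 × 3 = 12 strata average about 140/12 ≈ 12 patients per comparison.

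Replace the second censoring date with the last day with seizure data reported in IVRS during the blinded phase treatment period. This also covers withdrawn patients with no seizures.

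The cost is a few lines of text and a rerun on data already held. Because the addendum was written when withdrawal by arm was known, record the change as post hoc and keep the unadjusted result as supportive.
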